Combined elevations of AST or ALT and Total bilirubin^{b,d}	
For participants with normal baseline ALT and AST and TBL value: AST or ALT > 3.0 x ULN combined with TBL > 2.0 x ULN without evidence of cholestasis ^c Or hemolysis OR For participants with elevated baseline AST or ALT or TBL value: [AST or ALT > 3 x baseline] OR [AST or ALT > 8.0 x ULN], whichever is lower, combined with [TBL > 2 x baseline AND > 2.0 x ULN]	Mandatory: Permanently discontinue participant from study drug treatment
METABOLIC	
Amylase and/or lipase elevation	
Grade 1 (> ULN - 1.5 x ULN)	Maintain dose level
Grade 2 (> 1.5 - 2.0 x ULN; > 2.0 - 5.0 x ULN and asymptomatic)	Maintain dose level
Grade 3 (> 2.0 - 5.0 x ULN with signs or symptoms; > 5.0 x ULN and asymptomatic)	Omit the dose until resolved to \leq grade 2, then 
 • If resolved in \leq 14 days, resume treatment at the same dose level • If resolved in > 14 days, then \downarrow 1 dose level
Grade 4 (> 5.0 x ULN and with signs or symptoms)	Permanently discontinue participant from study drug treatment
CARDIAC	
Electrocardiogram QT corrected (QTc) interval prolonged	
Grade 1 (QTcF 450-480 ms) and	Maintain dose level

Grade 2 (QTcF 481-500 ms)	
Grade 3 (QTcF \geq 501 ms on at least two separate ECGs)	Omit dose until resolved to \leq grade 2, then: 
 • If resolved in \leq 7 days, resume treatment at the same dose level • If resolved in $>$ 7 days, then \downarrow 1 dose level
Grade 4 (QTcF \geq 501 or $>$ 60 ms change from baseline and Torsades de pointes or polymorphic ventricular tachycardia or signs/symptoms of serious arrhythmia)	Permanently discontinue participant from study drug treatment
GASTROINTESTINAL	
Pancreatitis	
Grade 2	Maintain dose level
Grade \geq 3	Permanently discontinue participant from study drug treatment
Diarrhea**	
Grade 1 (despite maximal anti-diarrheal medication)	Maintain dose level
Grade 2 (despite maximal anti-diarrheal medication)	Omit dose until resolved to \leq grade 1, then maintain dose level. 
 • If diarrhea returns as \geq grade 2, then omit dose until resolved to \leq grade 1, then resume treatment at \downarrow 1 dose level
Grade 3 or 4 (despite maximal anti-diarrheal medication)	Omit dose until resolved to \leq grade 1, then resume treatment at \downarrow 1 dose level
Vomiting	
Grade 1 (despite appropriate anti-emetics)	Maintain dose level

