Combined AST or ALT and Total bilirubin elevation without cholestasis or hemolysis	
 Combined elevations of AST or ALT and TBL: 
 After discontinuing the participant from capmatinib permanently, repeat LFTs as soon as possible, preferably within 48 hours from awareness of the abnormal results, then with weekly monitoring of LFTs, or more frequently if clinically indicated, until AST, ALT, or bilirubin have resolved to baseline or stabilization over 4 weeks. Core LFTs consist of ALT, AST, Gamma-glutamyl transferase (GGT), TBL (fractionated [direct and indirect], if TBL $> 2.0 \times$ ULN), and ALP (fractionated [quantification of isoforms], if ALP $> 2.0 \times$ ULN.)
METABOLIC	
Asymptomatic amylase or lipase \geq CTCAE grade 3	
 Test weekly (or more frequently) until \leq CTCAE grade 2. A CT scan or equivalent imaging procedure to assess the pancreas, liver, and gallbladder is recommended within 7 days of the first occurrence of any \geq CTCAE grade 3 result, to exclude disease progression or potential other liver or pancreatic disease.
CARDIAC	
\geq CTCAE grade 3	Test weekly (or more frequently) until \leq CTCAE grade 2.
QTcF \geq 501 ms (CTCAE grade 3)	
 When QTcF \geq 501 ms (CTCAE grade 3), perform the following: 
 Request an immediate manual read of the ECG. Perform an analysis of serum potassium, calcium, phosphorus, and magnesium, and if below lower limit of normal (LLN), correct with supplements to within normal limits. Review concomitant medication usage for the potential to prolong the QT-interval. Check compliance with correct dose and administration of capmatinib. Perform a repeat ECG within one hour of the first QTcF of \geq 501 ms. If QTcF remains \geq 501 ms, repeat ECG as clinically indicated, but at least once daily until the QTcF returns to $<$ 501 ms.

TOXICITY	FOLLOW-UP EVALUATION

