	
 Repeat ECGs 7 days and 14 days (and then every 21 days) after dose resumption for all participants who had therapy interrupted due to QTcF \geq 501 ms. If QTcF of \geq 501 ms recurs, repeat ECGs as described above. Notes: 
 The investigator should contact the Novartis Medical Lead or designee regarding any questions that arise if a participant with QTcF prolongation should be maintained on study. If the ECG report shows a QTcF \geq 501 ms (not previously documented on the site machine), contact the participant and instruct him/her to suspend capmatinib and return for a repeat ECG as soon as possible. Conduct a manual read of the repeat ECG immediately, and the above guidance followed.
GASTROINTESTINAL	
Diarrheal	
 Investigate potential concomitant medication, food or comorbidity driven causes of diarrhea (including infectious causes) and remedy these causes if possible (e.g. discontinuation of concomitant medication, dietary modification, treatment of comorbidity). The participant should be monitored for signs of dehydration and instructed to take preventive measures against dehydration as soon as diarrhea occurs. Antidiarrheal medication must be initiated at the first sign of abdominal cramping, loose stools or overt diarrhea. Concomitant medication for the treatment of diarrhea should follow local practice and the investigator's best judgment and may follow "the recommended guidelines for the treatment of cancer treatment-induced diarrhea" (Benson et al 2004). For example: 
 For uncomplicated diarrhea (grade 1 or 2 without complicating signs or symptoms), loperamide given at a standard dose (e.g. initial administration of 4 mg, then 2 mg every 2-4 hours, maximum of 16 mg/day), along with oral hydration and dietetic measures should be considered. Note: complicating signs or symptoms include moderate to severe cramping, decreased PS, fever, neutropenia, frank bleeding or dehydration. For complicated diarrhea (all grade 3 or 4, grade 1-2 with complicating signs or symptoms), management should involve intravenous (IV) fluids, and consider treatment with octreotide (at starting dose of 100 to 150 μg sub-cutaneous tid or 25 to 50 μg IV) and antibiotics (e.g. fluoroquinolone) should be given

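### Tables 6-3 and 6-4 define grade 3 QTc prolongation differently, so a single unconfirmed QTcF of 501 ms or more has no QTc row in one table and is grade 3 in the other

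*Protocol*

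**What the plan says.** Table 6-3 (Section 6.5, dose modifications) grades QTcF in steps. Grade 1 is 450 to 480 ms. The next row is "Grade 2 (QTcF 481-500 ms"; both carry an instruction to keep the dose. Grade 3 is a QTcF at or above "501 ms on at least two separate ECGs", with the action "Omit dose until resolved to" grade 2 or lower. Grade 4 is a QTcF of 501 ms or more, or more than a 60 "ms change from baseline and Torsades de pointes or polymorphic ventricular tachycardia or signs/symptoms of serious arrhythmia", with permanent discontinuation. Only the grade 3 row asks for more than one ECG.

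Table 6-4 (Section 6.5.2, follow-up evaluations) starts its cardiac steps at a QTcF at or above "501 ms (CTCAE grade 3), perform the following". One of those steps is "Perform a repeat ECG within one hour of the first QTcF of" 501 ms or more, so the grade 3 label is attached before any repeat exists. A separate note covers an ECG report at or above "501 ms (not previously documented on the site machine"; in that situation the site must "contact the participant and instruct him/her to suspend capmatinib and return for a repeat ECG as soon as possible".

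Three other places bear on this. Section 6.5 says that grade 3 treatment-related toxicity is interrupted until at least grade 1 and refers to Table 6-3 for the dose at restart. Section 6.5.1 says that when the drug is withheld for toxicity, Tables 6-3 and 6-2 apply. Section 8.4.4 asks for triplicates at the scheduled ECGs and for unscheduled ECGs with clinically significant findings.

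**The concern.** The toxicity grade decides whether dosing is held and how it restarts, and Section 6.5 bases every dose change on the worst preceding grade. If one grade has two definitions, two sites can both follow the protocol and grade the same tracing differently.

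The participant affected has one reading of 501 ms or more, a lower repeat and no arrhythmia feature. Table 6-4 calls that reading grade 3. Table 6-3 cannot: it is above the grade 2 limit, it lacks the second ECG for grade 3, and it lacks the arrhythmia feature for grade 4. What is at stake is consistent handling of a cardiac safety signal and consistent AE grading.

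**Working it through.** The plan gives no figure to reproduce here, so the check sets the two tables side by side and then follows the restart path.

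**Step 1. Classify each situation under both tables.**

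| Situation (QTcF of 501 ms or more) | Table 6-3 | Table 6-4 |
|---|---|---|
| One reading seen on site, repeat lower, no arrhythmia feature | No QTc row fits | Grade 3; work-up and repeat within one hour; nothing on holding the dose |
| One reading on an ECG report, not already documented on the site machine, repeat lower, no arrhythmia feature | No QTc row fits | Grade 3; suspend and recall for repeat |
| One reading with an arrhythmia feature | Grade 4, discontinue | Work-up steps apply |
| Two separate ECGs, no arrhythmia feature | Grade 3, omit dose | Grade 3; ECG at least daily until below 501 ms |

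The tables agree in the last row. The first two rows show the mismatch in grade, and only the second involves a dose already stopped.

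**Step 2. Follow the restart in the recall case.** Capmatinib is suspended and the repeat is lower. Section 6.5.1 sends the site to Table 6-3. Four readings are then open:

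- Grade the repeat alone. At 500 ms or below it falls in a row that keeps the dose, or in none. But Section 6.5 grades on the worst preceding toxicity, which is the first reading.
- Borrow the grade 3 QTc row although its two-ECG condition is not met. Restart is then possible at grade 2 or lower, that is, at 500 ms or below.
- Use the general grade 3 rule in Section 6.5. Restart then waits for grade 1, that is, 480 ms or below.
- Use the row in Table 6-3 for other AEs. At grade 3 it also waits for grade 1 or lower, and it sets one dose level lower. QTc has rows of its own, so this is not an obvious reading.

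The second and third readings part when the repeat is 481 to 500 ms. The second allows restart and the third does not. Under the third, the unconfirmed reading faces a stricter restart condition than a confirmed one.

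**Step 3. Check what counts as a separate ECG.** If tracings within one triplicate count as separate, two of three at or above 501 ms meet Table 6-3 at once. If they do not, a further recording is needed. Neither table says. Exclusion criterion 6 in Section 5.2 uses the mean of a triplicate for the screening ECG, but no such convention is stated for ECGs on treatment.

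**Step 4. Check how often this can arise and what it feeds.** Section 8.4.4 schedules ECGs at screening, before the first dose and at end of treatment, so a reading between first dose and end of treatment comes from an unscheduled ECG. SAP Section 4 reports 4 participants enrolled and replaces the planned summaries by listings. The only AE tables in SAP Section 2.8.1 are by system organ class and preferred term, without grade. The documents give no rate of QTcF readings of 501 ms or more.

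**The case against.** The strongest reply is that the tables work in sequence. Table 6-3 governs dosing and Table 6-4 governs follow-up. The one-hour repeat supplies the second ECG that Table 6-3 asks for, and with doses about 12 hours apart (Section 6.7.2) a dose is unlikely to fall between the two recordings. Sections 6.5 and 6.5.1 both direct dose action to Table 6-3, so a governing table is named. This largely answers the case of a reading seen on site. It does not answer the recall case, where the dose has already been stopped under Table 6-4 and the governing table has no matching row.

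Three stronger readings are tempting, and the documents do not support them.

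- A reader might infer that Table 6-4 stops dosing on any single reading of 501 ms or more. It does so only for a report value not previously documented on the site machine; the steps for other readings contain no hold. The ECG schedule after resumption likewise applies only where therapy was interrupted.
- A reader might infer that the mismatch leaves the start of the 7-day clock undefined, and with it the restart dose. That resolution wording recurs in many Table 6-3 rows and is not specific to QTc. On site, the repeat is due within an hour.
- A reader might infer a visible effect on results, since one event among 4 participants is 1/4 = 25%. No planned table reports AEs by grade. AEs are graded by CTCAE version 5.0 (Section 10.1.1), and the protocol's QT summary uses absolute limits or changes from baseline (Section 12.5.2).

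**Conclusion.** The inconsistency stands in a narrow form. Grade 3 QTcF prolongation has two incompatible definitions, and one unconfirmed reading without an arrhythmia feature falls between them. The practical consequence is largely confined to the recall case, where the drug is suspended before confirmation and the text offers no matching restart row and two different resolution thresholds. For on-site readings the difference is mainly one of grade label.

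The effect is on safety conduct and AE grading. That the case is rare is an inference from the sparse ECG schedule and the 4 participants enrolled, since no rate is given. No efficacy estimate, error rate or planned summary moves. It is still worth correcting, because the rule decides whether a drug is held for a cardiac signal and the correction is wording only.

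**What to change.** Reconcile Table 6-3, Table 6-4 and the general grade 3 text in Section 6.5 so that one definition of grade 3 QTcF prolongation applies throughout. The reconciled text should settle three things: how a first, unconfirmed reading is graded and handled, including after a suspension under the Table 6-4 note; which resolution threshold then applies; and whether tracings within a triplicate count as separate ECGs. Whether this is done by a row, a footnote or a cross-reference, and which clinical rule is adopted, is for the sponsor.

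The cost is a change of wording in two tables and one paragraph, with a short memo to sites. The reconciliation itself calls for no new data collection and no change to the analysis.

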6.5.1 Treatment interruption and treatment discontinuation

If the administration of capmatinib is temporarily interrupted for reasons other than toxicity, then treatment with capmatinib may be resumed at the same dose. If the treatment with capmatinib is withheld due to toxicity, the dose modification guidelines in [Table 6-3](#) & [Table 6-2](#) should be followed. In any case, scheduled visits and all assessments (including tumor assessments) should continue to be performed, as described in [Table 8-1](#).

If the treatment with capmatinib is withheld for more than 21 consecutive days (counting from the first day when a dose was interrupted), excluding the surgical and adjuvant chemotherapy

window specified below, then capmatinib should be permanently discontinued. Under exceptional circumstance, when the investigator believes that continuing treatment may still derive clinical benefit for the participant, study treatment may be resumed. However, the investigator must discuss and receive approval from Novartis Medical Lead or designee prior to continuing capmatinib treatment.

Participants who discontinue the study due to a study drug related AE or an abnormal laboratory value must be followed as described in [Section 6.5.2](#).

After the 8 week neoadjuvant treatment with capmatinib, participants are to undergo surgical resection. Participants should undergo within 2 weeks after last dose of neoadjuvant capmatinib. In addition, participants may receive adjuvant chemotherapy prior to re-starting capmatinib at the discretion of the investigator. For patients who do not receive adjuvant chemotherapy no more than 10 weeks should elapse from the date of surgery and the start of adjuvant capmatinib. For patients who do receive adjuvant chemotherapy, see [Section 6.2.1.1](#) for the dosing window. If participants for any reason cannot re-start capmatinib therapy within the specified windows, then study treatment must be permanently discontinued.

Participants who discontinue the study due to a surgery related AE must complete the EOT visit and safety follow-up visit.

6.5.2 Follow-up for toxicities

All participants will be followed for safety until 30 days after the last dose of capmatinib. Participants whose treatment is temporarily interrupted or permanently discontinued due to a toxicity AE or abnormal laboratory value must be followed until resolution or stabilization of the event, whichever comes first, including all study assessments appropriate to monitor the event.

An unscheduled assessment should be performed in all cases below where toxicity monitoring is recommended more frequently than defined by the schedule of assessments. Subsequent monitoring must be performed as per the regular visit schedule. Please refer to [Table 6-4](#) for follow-up evaluations for selected toxicities.

Table 6-4 Follow-up evaluations for selected toxicities

TOXICITY	FOLLOW-UP EVALUATION
HEMATOLOGICAL	
Febrile neutropenia, Neutropenia \geq CTCAE grade 3	
• Test weekly (or more frequently if clinically indicated) until \leq CTCAE grade 2.
Thrombocytopenia \geq CTCAE grade 3	
Anemia \geq CTCAE grade 3	
• Perform physical exam for check on bruising in case of major thrombocytopenia.
RENAL	
Serum creatinine \geq CTCAE grade 2	
• Test weekly (or more frequently if clinically indicated) until \leq CTCAE grade 1 or baseline.• Participants will be instructed to increase hydration until resolution to \leq CTCAE grade 1 or baseline.

TOXICITY	FOLLOW-UP EVALUATION
HEPATIC	
Isolated Total bilirubin elevation	
TBL CTCAE Grade 1:
 
 Monitor LFTs per protocol or more frequently if clinically indicated 
TBL CTCAE Grade 2:
 
 Weekly monitoring of LFTs, or more frequently if clinically indicated, until resolved to $\leq 1.5 \times$ ULN 
TBL CTCAE Grade 3:
 
 Weekly monitoring of LFTs, or more frequently if clinically indicated, until resolved to $\leq 1.5 \times$ ULN. If resolved in > 7 days, after discontinuing the participant from capmatinib permanently, the participant should be monitored weekly (including LFTs), or more frequently if clinically indicated, until TBL have resolved to baseline or stabilization over 4 weeks 
TBL CTCAE Grade 4:
 
 After discontinuing the participant from capmatinib permanently, the participant should be monitored weekly (including LFTs), or more frequently if clinically indicated, until TBL have resolved to baseline or stabilization over 4 weeks
Isolated AST/ALT elevation	
 AST/ALT CTCAE Grade 2 elevation: 
 For participants with baseline value $\leq 3.0 \times$ ULN: repeat LFTs as soon as possible, preferably within 48-72 hours from awareness of the abnormal results; if abnormal lab values are confirmed upon the repeat test, then monitor LFTs weekly, or more frequently if clinically indicated, until resolved to $\leq 3.0 \times$ ULN For participants with baseline value $> 3.0 \times$ ULN: monitor LFTs per protocol or more frequently if clinically indicated AST/ALT CTCAE Grade 3 elevation: 
 For AST/ALT elevation $> 5.0 - 10.0 \times$ ULN: For participants with baseline value $\leq 3.0 \times$ ULN: repeat LFTs as soon as possible, preferably within 48-72 hours from awareness of the abnormal results; monitor LFTs weekly, or more frequently if clinically indicated, until resolved to $\leq 3.0 \times$ ULN For participants with baseline value $> 3.0 \times$ ULN: repeat LFTs as soon as possible, preferably within 48-72 hours from awareness of the abnormal results; if abnormal lab values are confirmed upon the repeat test, then monitor LFTs, weekly, or more frequently if clinically indicated, until resolved to $\leq 5.0 \times$ ULN For AST/ALT elevation $> 10.0 - 20.0 \times$ ULN: 
 Repeat LFTs as soon as possible, preferably within 48-72 hours from awareness of the abnormal results;

TOXICITY	FOLLOW-UP EVALUATION
	
monitor LFTs weekly, or more frequently if clinically indicated, until resolved to \leq baseline
 
 AST/ALT CTCAE Grade 4 elevation: 
 Repeat LFTs as soon as possible, preferably within 48-72 hours from awareness of the abnormal results; monitor LFTs weekly, or more frequently if clinically indicated, until resolved to baseline or stabilization over 4 weeks.
Combined AST or ALT and Total bilirubin elevation without cholestasis or hemolysis	
 Combined elevations of AST or ALT and TBL: 
 After discontinuing the participant from capmatinib permanently, repeat LFTs as soon as possible, preferably within 48 hours from awareness of the abnormal results, then with weekly monitoring of LFTs, or more frequently if clinically indicated, until AST, ALT, or bilirubin have resolved to baseline or stabilization over 4 weeks. Core LFTs consist of ALT, AST, Gamma-glutamyl transferase (GGT), TBL (fractionated [direct and indirect], if TBL $> 2.0 \times$ ULN), and ALP (fractionated [quantification of isoforms], if ALP $> 2.0 \times$ ULN.)
METABOLIC	
Asymptomatic amylase or lipase \geq CTCAE grade 3	
 Test weekly (or more frequently) until \leq CTCAE grade 2. A CT scan or equivalent imaging procedure to assess the pancreas, liver, and gallbladder is recommended within 7 days of the first occurrence of any \geq CTCAE grade 3 result, to exclude disease progression or potential other liver or pancreatic disease.
CARDIAC	
\geq CTCAE grade 3	Test weekly (or more frequently) until \leq CTCAE grade 2.
QTcF \geq 501 ms (CTCAE grade 3)	
 When QTcF \geq 501 ms (CTCAE grade 3), perform the following: 
 Request an immediate manual read of the ECG. Perform an analysis of serum potassium, calcium, phosphorus, and magnesium, and if below lower limit of normal (LLN), correct with supplements to within normal limits. Review concomitant medication usage for the potential to prolong the QT-interval. Check compliance with correct dose and administration of capmatinib. Perform a repeat ECG within one hour of the first QTcF of \geq 501 ms. If QTcF remains \geq 501 ms, repeat ECG as clinically indicated, but at least once daily until the QTcF returns to $<$ 501 ms.

TOXICITY	FOLLOW-UP EVALUATION
	
 Repeat ECGs 7 days and 14 days (and then every 21 days) after dose resumption for all participants who had therapy interrupted due to QTcF \geq 501 ms. If QTcF of \geq 501 ms recurs, repeat ECGs as described above. Notes: 
 The investigator should contact the Novartis Medical Lead or designee regarding any questions that arise if a participant with QTcF prolongation should be maintained on study. If the ECG report shows a QTcF \geq 501 ms (not previously documented on the site machine), contact the participant and instruct him/her to suspend capmatinib and return for a repeat ECG as soon as possible. Conduct a manual read of the repeat ECG immediately, and the above guidance followed.
GASTROINTESTINAL	
Diarrheal	
 Investigate potential concomitant medication, food or comorbidity driven causes of diarrhea (including infectious causes) and remedy these causes if possible (e.g. discontinuation of concomitant medication, dietary modification, treatment of comorbidity). The participant should be monitored for signs of dehydration and instructed to take preventive measures against dehydration as soon as diarrhea occurs. Antidiarrheal medication must be initiated at the first sign of abdominal cramping, loose stools or overt diarrhea. Concomitant medication for the treatment of diarrhea should follow local practice and the investigator's best judgment and may follow "the recommended guidelines for the treatment of cancer treatment-induced diarrhea" (Benson et al 2004). For example: 
 For uncomplicated diarrhea (grade 1 or 2 without complicating signs or symptoms), loperamide given at a standard dose (e.g. initial administration of 4 mg, then 2 mg every 2-4 hours, maximum of 16 mg/day), along with oral hydration and dietetic measures should be considered. Note: complicating signs or symptoms include moderate to severe cramping, decreased PS, fever, neutropenia, frank bleeding or dehydration. For complicated diarrhea (all grade 3 or 4, grade 1-2 with complicating signs or symptoms), management should involve intravenous (IV) fluids, and consider treatment with octreotide (at starting dose of 100 to 150 μg sub-cutaneous tid or 25 to 50 μg IV) and antibiotics (e.g. fluoroquinolone) should be given
Nausea and Vomiting	
 The investigator should consider/investigate potential concomitant medication, food or comorbidity driven causes of nausea and/or vomiting and remedy these causes if possible

TOXICITY	FOLLOW-UP EVALUATION
	
(e.g. discontinuation of concomitant medication, dietary modification, treatment of comorbidity).
 
 Individualized supportive and anti-emetic treatment should be initiated, as appropriate, at the first signs and/or symptoms of these AEs. In participants with vomiting, the participant should be monitored for signs of dehydration and instructed to take preventive measures against dehydration. Concomitant medication for the treatment of nausea and/or vomiting should follow local practice and the investigator's best judgment.
SKIN TOXICITY	
Rash and Photosensitivity	
CTCAE grade 1	Consider to initiate institute appropriate skin toxicity therapy (such as antihistamines, topical corticosteroids and low-dose systemic corticosteroids)
CTCAE grade 2	Initiate/intensify appropriate skin toxicity therapy (such as antihistamines, topical corticosteroids and low-dose systemic corticosteroids).
\geq CTCAE grade 3	Intensify appropriate skin toxicity therapy and monitor weekly or more frequently until resolved to grade \leq 2
Peripheral edema	
CTCAE grade \leq 2	Consider to initiate conservative measures such as leg elevation, compression stockings, and dietary salt modification as clinically indicated.
CTCAE grade \geq 3	Initiate/intensify conservative measures
RESPIRATORY, THORACIC AND MEDIASTINAL DISORDERS	
ILD/Pneumonitis	
CTCAE Grade 1	
 CT scan (high-resolution with lung windows) recommended, with serial imaging to monitor for resolution or progression-re-image at least every 3 weeks Monitor for symptoms every 2-3 days - Clinical evaluation and laboratory work-up for infection Monitoring of oxygenation via pulse oximetry recommended Consultation of pulmonologist recommended
CTCAE Grade 2	
 CT scan (high-resolution with lung windows) Monitor symptoms daily, consider hospitalization Clinical evaluation and laboratory work up for infection Consult pulmonologist Pulmonary function tests ^a - if normal at baseline, repeat every 8 weeks Bronchoscopy with biopsy and/or BAL recommended ^c Symptomatic therapy including corticosteroids if clinically indicated (1 to 2 mg/kg/day prednisone or equivalent as clinically indicated) ^b

TOXICITY	FOLLOW-UP EVALUATION
CTCAE Grade 3 and Grade 4	
 • Computerized Tomography (CT) scan (high-resolution with lung windows) • Clinical evaluation and laboratory work-up for infection • Consult pulmonologist • Pulmonary function tests^a-if < normal, repeat every 8 weeks until \geq normal • Bronchoscopy with biopsy and/or BAL if possible^c • Treat with IV steroids (methylprednisolone 125 mg) as indicated. When symptoms improve to \leq Grade 1, a high dose oral steroid (prednisone 1 to 2 mg/kg once per day or dexamethasone 4 mg every 4 hours)^b. • If IV steroids followed by high dose oral steroids does not reduce initial symptoms within 48 to 72 hours, consider non-corticosteroid immunosuppressive medication

^a PFT (Pulmonary function tests) to include: diffusing capacity of lungs for carbon monoxide corrected for hemoglobin (DLCO); spirometry; resting oxygen saturation

Guideline for significant deterioration in lung function: Decrease in spirometry and/or DLCO of 30% and/or O₂ saturation \leq 88% at rest on room air.

^b Duration and dose of course of corticosteroids will vary according to circumstances but should be as limited as possible. Consider tapering dosage at end.

^c If bronchoscopy is performed, bronchoalveolar lavage (BAL) should be done where possible to exclude alveolar haemorrhage, opportunistic infections, cell count + determination lymphocyte CD4/8 count where possible.

